Appendix 1b:Chronic Liver Failure Consortium (CLIF-C) Scoring Systems

CLIF-C Organ Failure (CLIF-C OF) Scoring System

Organ System	Score = 1	Score = 2	Score = 3
Liver (mg/dl)	Bilirubin < 6	6 ≤ Bilirubin ≤ 12	Bilirubin >12
Kidney (mg/dl)	Creatinine <2	Creatinine ≥2 <3.5	Creatinine ≥3.5 or renal replacement
Brain (West-Haven)	Grade 0	Grade 1-2	Grade 3-4
Coagulation	INR < 2.0	2.0 ≤ INR < 2.5	INR ≥ 2.5
Circulation	MAP ≥70 mm/Hg	MAP <70 mm/Hg	MAP < 65 mmHg; Vasopressors
Respiratory: PaO2/FiO2 or SpO2/FiO2	>300 >357	≤300 - > 200 >214- ≤357	≤200 ≤214

The shaded areas represent 'Organ Failures'

From: Jalan R, Saliba F, Pavesi M, Amoros A, Moreau R, Gines P, et al. Development and validation of a prognostic score to predict mortality in patients with acute-on-chronic liver failure. Journal of Hepatology 2014; 61: 1038–1047

CLIF-C Acute Decompensation (CLIF-C AD) Formula

10*0.03*Age + 0.66*Ln Creatinine + 1.71*Ln INR + 0.88*Ln WBC +-0.05*Sodium + 8

From: Jalan R, Pavesi M, Saliba F, Amoros A, Fernandez J, Holland-Fischer P, et al. The CLIF Consortium Acute Decompensation score (CLIF-C ADs) for prognosis of hospitalised cirrhotic patients without acute-onchronic liver failure. Journal of Hepatology 2015; 62: 831–840

CLIF-C Acute-on-Chronic Liver Failure (CLIF-C ACLF) Formula

10*[0.33*CLIF-OFs + 0.04*Age + 0.63*Ln WCC - 2]

From: Jalan R, Saliba F, Pavesi M, Amoros A, Moreau R, Gines P, et al. Development and validation of a prognostic score to predict mortality in patients with acute-on-chronic liver failure. Journal of Hepatology 2014: 61: 1038–1047

Clinical Investigation Plan CIP YAQ-002 Version: 7.0 10 0	October 2019
---	--------------

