- Replacement fluid (pre-dilution solution) to start at a rate of 1000 ml/hr and increased gradually to up to 3500 mls/hr (50mls/kg/hr for a 75 kg person) subject to haemodynamic stability. Concomitant dialysis component to run at 1500 mls/hr (25 ml/kg/hr for a 75 kg person).
- Albumin is exchanged simultaneously with DIALIVE treatment. Infusion of fresh albumin will be through the HepAlbin filter at a rate of 5 g/hr (to replace albumin removed by the device). This equates to an infusion of 20% human albumin solution at a rate of 25mls/hr.
- Mean arterial pressure is to be continuously monitored, and MAP is maintained at 90% or higher of pretreatment MAP or above 65 mmHg, whichever is higher.
- 2-hourly blood gas analysis (including lactate), and 4 hourly other bloods (FBC, U/E, LFT, coagulation) at 0, 4 and 8-12 hrs (end of treatment) should be performed.
- A senior staff member will closely supervise the dialysis procedure during the first few hours of treatment, with a clear internatl escalation plan available, and discuss with study CI where necessary
- Effluent of dialysis fluid from the effluent line AND waste collection bag to be collected a 0-1, 4, 8-10 hrs (end of treatment) as part of biobank samples.

- Following completion of treatment session:

- Blood within the circuit is to be returned back to the patient, unless the filter is clotted.
- Repeat Haemolysis screen (at end of session of D1 only)
- EAA-analysis (end of days 1, 2 and 3)
- Ensure treatment data is stored in the device and retrieved at a later date
- Blood to be collected as part of biobank samples. (end of days 1, 2, 3)

2.3 Details concerning the manufacturer and traceability of the investigational device.

Membrane ⁹ :	septeX™ Haemofilter	oXiris® Haemofilter
Manufacturer:	Baxter, USA	Baxter, USA
Indications:	Continuous renal replacement therapy for subjects with acute renal failure	For subjects who have acute renal failure, fluid overload or both.
Intended use:	Continuous veno-venous haemodialysis (CVVHD) in conditions where the removal of plasma components with molecular weights up to a value of 45 kDa, such as substances that mediate inflammation, is indicated	Veno-venous therapies: slow continuous ultrafiltration (SCUF); continuous veno-venous haemofiltration (CVVH); continuous veno-venous haemodialysis (CVVHD); continuous veno-venous haemodiafiltration (CVVHDF)

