	complete by clamping off oXiris® dialysing fluid-effluent circuit
	Operation
	Prismaflex control, monitoring and safety features all engaged
	 CVVHDF proceeds as indicated except blood path series connection of septeX[™] and oXiris®
	ICU/HD monitoring per CIP and institutional standard of care
	Restitution of all extracorporeal blood during

Clinical Investigation Plan

CIP YAQ-002

Version: 7.0 10 October 2019

	Clinical Investigation Plan	CIP YAQ-002		Version: 7.0 10 October 2019
				 
				d at end of session, except in case of filter thing.
Circumventing of Prismaflex monitoring and control features:		Function	onal compatibility of Prismaflex, septeX™	
-	LDD adverse events		set + o	(iris® set verified in porcine model
- exanguination - thromboembolism		Prisma	iflex pre-programmed sequential	

clotting exacerbation of symptoms and complications of liver failure

death

mistakes Prismaflex control, monitoring and safety features

procedures mostly eliminate slips, lapses and

Prismaflex CE marked for CVVHDF

engaged

Investigator familiarity with CVVHDF

Use is restricted to qualified investigator and supervised qualified support familiar with aseptic technique and liver failure patients

Blood loss due to venous cannulation

- Undertaken by experienced staff trained in the procedure
- Standard clinical procedures are followed
- Coagulation results reviewed prior to cannulation
- CIP specifies ICU/HDU monitoring particularly monitoring:
 - liver function
 - cardiovascular function
 - renal function

Hypotension induced by DIALIVE, especially in patients who may be intravascularly depleted because of fluid restriction, diuretic therapy, inadequate oral intake and anemia, or those with evidence of vasoplegia.

- perform fluid preloading
- simultaneous replacement of lost albumin
- stepwise increase of blood flow rate through the **DIALIVE**
- stepwise increase of replacement fluid
- closely monitor the patient

3.3 Residual risks associated with participation in the clinical investigation.

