5.1.3 Secondary End Points

To evaluate the performance of the DIALIVE in patients with ACLF. This is measured by;

Change in Plasma endotoxin level (endotoxin activity and concentration) between;

D1, D3, D5 and D10 across SOC arm $\,$

D1, D3, D5 and D10 across DIALIVE arm

_

¹⁰ In case a patient's treatment is discontinued, the follow up period will remain 28 days from the moment of randomization.

Clinical Investigation Plan	CIP YAQ-002	Version: 7.0 10 October 2019
-----------------------------	-------------	------------------------------

Start and end of a treatment session (on D1, D2 and D3) with DIALIVE D1,D3, D5 and D10 between SOC and DIALIVE arms for patients presenting with the same grades of ACLF (i.e. Grade 1 ALCF compared with Grade 1 ACLF)

Target-Value (TV): 40% reduction; Acceptable-Value (AV): 20% reduction at end of treatment cycle.

• Change in Albumin function (Human non-mercapt albumin -2 (HNA-2) / Human marcapt albumin (HMA) ratio:

D1, D3, D5 and D10 across SOC arm
D1,D3, D5 and D10 across DIALIVE arm
Start and end of a treatment session (on D1, D2, D3) with DIALIVE
D1,D3, D5 and D10 between SOC and DIALIVE arms for patients presenting with the same grades of ACLF (i.e. Grade 1 ALCF compared with Grade 1 ACLF)

TV: 40% reduction; AV: 20% reduction at end of treatment cycle.

- Mortality: 28-days and 90 days
- Change in ACLF Grade
- Change in CLIF-ACLF score
- Improvement in individual organ function: Brain (HE), Kidney (creatinine), CVS (mean arterial pressure), Pulmonary (P/F ratio, or S/F if patient is not intubated), Liver (serum bilirubin) and coagulation (INR and platelets).
- Status at ICU and Hospital Discharge (including discharge to a hospice for palliative care).
- Lengths of stay in ICU and Hospital at D28 and D90
- ICU and Hospital re-admissions with another episode of ACLF up to 3 months after randomisation.

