5.3.3. Criteria and procedures for subject withdrawal or discontinuation

Other than those required for liver dialysis, no additional Investigation or interventions are expected over and above the routine SOC, which the patient will continue to receive. It is anticipated, therefore, that all subjects will continue to be highly compliant with the CIP study procedures. Non-compliance with the CIP study procedures will be documented by the investigator and reported to the Sponsor as agreed. Persistent non-compliance may lead to be withdrawn of the patient from the study.

The participant may, however, voluntarily choose to withdraw from the study at any time for any reason. This will not in any way affect their routine care. If the participant loses capacity during the study, the legal representative (if appointed) also has the right to withdraw the participant in this instance, acting on the presumed wishes of the participant.

The investigator also has the right to withdraw a patient at any time due to failure to follow CIP, administrative, safety or other reason. Stopping rules (for the study and for the DIALIVE treatment) have been developed as follows:

- A) Rules for discontinuing DIALIVE therapy during a treatment session, based on safety grounds
 - a. Persistent shock (MAP < 65mmHg or < 90% pre-treatment value, whichever is higher) for > 2 hrs with features of tissue hypoperfusion, unresposive to volume resuscitation and/or low dose noradrenaline (0.1µg/kg/min). Treatment can be restarted once haemodynamic stability is restored.
 - b. Deteriorating respiratory failure as defined by worsening PaO₂/FiO₂ to < 200 mmHg (27 kPa) and SaO₂/FiO₂ to < 214. Treatment can be recommenced following a 12 hour recovery period.
 - c. Disseminated Intravascular Coagulation (DIC). Thrombocytopenia alone (to below exclusion criterion threshold) without evidence of DIC is not a stopping rule. Platelet treatment should be considered in this case.
 - d. Progression to more than 3 organ failures

Clinical Investigation Plan CIP YAQ-002 Version: 7.0 10 October 20	19
--	----

- e. In the opinion of the PI, the treatment is unsafe to continue
- B) Study stopping rules for patients randomized to either the SOC or the DIALIVE arm
 - a. Withdrawal of patient consent by the patient (or if applicable the appointed respresentative, where the patient were to lose capacity during this process).

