Appendix 1a- Acute-on-Chronic Liver Failure Grading Scheme per CLIF-OF scoring system.

Grade	Subgroups	ACLF grade equivalent (for DIALIVE study)
No ACLF*	 Patients with no organ failure Patients with a single hepatic, coagulation, circulation or respiratory failure, no AKI and no HE serum creatinine <1.5mg/dL and no hepatic encephalopathy (HE) Patients with single cerebral failure and serum creatinine <1.5mg/dL 	
Grade 1	 Patients with renal failure (sCr > 2 mg/dL) Patients with other single failure organ failure with serum creatinine ≥1.5 and <2 mg/dl and/or HE grade 1-2 	 Patients with serum bilirubin > 20 mg/dL (364 μmol/L) AKI stage 1b (sCr > 1.5 mg/dL or 134 μmol/L)
Grade 2	Patients with 2 organ failures	
Grade 3 a	Patients with 3 organ failures	
Grade 3 b	Patisents with more than 3 organ failure	

From: Moreau, R., et al., *Acute-on-chronic liver failure is a distinct syndrome that develops in patients with acute decompensation of cirrhosis.* Gastroenterology, 2013. **144**(7): p. 1426-37, 1437 e1-9.

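### After a DIALIVE session, creatinine and the scores built on it cannot be told apart from device clearance, yet their change is summarised by arm at every visit as clinical benefit

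*Protocol*

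**What the plan says.** **Endpoints.** Section 5.1.3 lists change in ACLF grade, change in CLIF-ACLF score and "Improvement in individual organ function: Brain (HE), Kidney (creatinine") as secondary endpoints. The Synopsis groups them under clinical benefit of DIALIVE plus standard of care (SOC) against SOC alone. Section 5.1.4 adds MELD and serum creatinine as exploratory. Section 6 summarises change from baseline at each visit, by arm, descriptively.

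**Scores.** Appendix 1b gives kidney score 1 for creatinine below 2 mg/dL, 2 from 2 to below 3.5, and 3 for "Creatinine ≥3.5 or renal replacement". The CLIF-C ACLF score is "10*[0.33*CLIF-OFs + 0.04*Age + 0.63*Ln WCC - 2"]. Appendix 1a grades by number of organ failures (grade 2 is "Patients with 2 organ failures") and takes creatinine above 2 mg/dL as renal failure.

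**Device.** The set-up text in Section 3.2 says "CVVHDF proceeds as indicated except blood path series connection". Section 2.2 gives the flows: "Replacement fluid (pre-dilution solution) to start at a rate of 1000 ml/hr and increased gradually to up to 3500 mls/hr", and "Concomitant dialysis component to run at 1500 mls/hr". A session lasts 8 to 10 h, on three consecutive days within a 10-day window. Section 2.2 expects the dialysis component to delay or avoid CRRT, and allows CRRT for renal failure in both arms.

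**Timing.** Section 5.4 schedules the scores on Days 1, 3, 5, 10, 14 and 28 in both arms, and also on Day 2 in the DIALIVE arm. It fixes pre-session and post-session sampling for the biomarkers, but not for the Day 2 and Day 3 blood that feeds the scores.

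**The concern.** The assigned treatment acts directly on the measurement. A fall in creatinine on or soon after a treatment day may mean recovering kidneys, removal by the filter, or both. Only one arm has the filter by design. SOC patients may receive CRRT, but Appendix 1b then sets their kidney score to 3. A DIALIVE patient spared CRRT by the device may instead be scored on dialysed creatinine.

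The scoring rule adds a second ambiguity, because Appendix 1b does not say whether a DIALIVE session is renal replacement. If sites differ, some DIALIVE patients shift up and others down for reasons unrelated to their kidneys.

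At stake is the reading of clinical-benefit endpoints in a first-in-man study of 15 evaluable patients per arm, whose results are meant to shape later trials.

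**Working it through.** The plan states no figure to reproduce here. Two checks apply: the score arithmetic, and the size of creatinine removal at the protocol's own flows.

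**1. Score arithmetic (Appendix 1b and Appendix 3)**

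- Change in CLIF-C ACLF = 10 × 0.33 × change in kidney sub-score.
- One step (3→2 or 2→1): 10 × 0.33 × 1 = 3.3 points. Two steps (3→1): 6.6 points.
- Two steps need creatinine to go from at least 3.5 to below 2 mg/dL, a fall of more than 1 − 2/3.5 = 43%.
- Crossing 2 mg/dL also removes one organ failure under Appendix 1a, which can lower the grade by one step.
- Change in MELD = 9.6 × ln(creatinine ratio).

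**2. Creatinine removal in one session**

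Formula: C_post/C_pre = exp(−K·t/V).

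- t = 8 to 10 h (Section 2.2).
- V = 0.5 to 0.6 L/kg × 75 kg = 37.5 to 45 L. This is an assumption; the documents give no volume.
- K, dialysis flow only = 1.5 L/h.
- K, maximum flows = 1.5 + 3.5 = 5.0 L/h. Corrected for pre-dilution at the maximum blood flow of 250 mL/min (15 L/h): 5.0 × 15/(15 + 3.5) = 4.05 L/h.
- Assumption: effluent is fully saturated with creatinine. Section 2.9 reports effective in-vitro clearance of small molecules but does not name creatinine.

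| Case | Smallest effect (8 h, 45 L) | Largest effect (10 h, 37.5 L) |
|---|---|---|
| Dialysis flow only | exp(−0.267) = 0.766, fall 23%, MELD −2.6 | exp(−0.400) = 0.670, fall 33%, MELD −3.8 |
| Maximum flows, corrected | exp(−0.721) = 0.486, fall 51%, MELD −6.9 | exp(−1.081) = 0.339, fall 66%, MELD −10.4 |

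Replacement fluid starts at 1000 mL/h and is stepped up, so real sessions should lie between the two rows.

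**3. Three daily sessions with native kidney function held constant**

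Further assumptions: creatinine generation 1 g/day, V = 45 L, 8 h sessions, native clearance set so that the starting value would stay steady without the device. Values are in mg/dL; the first figure is dialysis flow only, the second maximum flows.

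| Start | Before Day 3 session | After Day 3 session | Day 5 | Day 10 |
|---|---|---|---|---|
| 3.6 | 2.88 / 2.19 | 2.39 / 1.35 | 3.17 / 2.80 | 3.58 / 3.56 |
| 2.5 | 2.13 / 1.75 | 1.78 / 1.10 | 2.34 / 2.18 | 2.50 / 2.50 |

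- Start 3.6: the kidney score goes from 3 to 2 before the Day 3 session, and to 2 or 1 after it. On Day 5 it is still 2. By Day 10 it is 3 again.
- Start 2.5: the renal failure disappears on paper after the Day 3 session, and before it at maximum flows.
- In the 3.6 example Day 5 is 40 h after the last session ended, and creatinine is still 12% (3.17/3.6) to 22% (2.80/3.6) low.

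**4. The literal reading of Appendix 1b**

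If DIALIVE counts as renal replacement, the kidney sub-score goes 1→3 (+6.6 points) or 2→3 (+3.3 points). A patient without renal failure gains one organ failure.

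**The case against.** Several points on the other side stand.

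- **DIALIVE is probably not meant to count as renal replacement.** A reader might infer that every DIALIVE patient scores kidney failure on each treatment day. Section 2.2 argues against this: it treats CRRT as a separate treatment given after a session, and speaks of additional CRRT. The upward shift therefore belongs to the weaker reading. But Section 2.2 gives no scoring rule, and if DIALIVE does not count, the clearance problem applies in full.
- **Day 1 is not affected.** Pre-samples are taken just before connection (Section 2.2), and the schedule requires Day 1 tests before treatment if it starts on Day 0. Day 1 is baseline.
- **Not every patient is affected.** Someone starting below 2 mg/dL shows a change in creatinine and MELD but not in the kidney sub-score, and 6.6 points is the maximum case. Grade can still move, because Appendix 1a also uses a cut at 1.5 mg/dL for single non-renal failures.
- **All analysis is descriptive, and off-device visits already exist.** True, so the remedy is cheap. A descriptive arm difference labelled as clinical benefit can still mislead.
- **The SAP, not shown, may hold a derivation rule.** Possibly. But the score is defined in the protocol, and Section 6 itself fixes the visit-by-visit summary by arm.

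A reader might also infer that a grade 3a patient with three non-renal failures meets "Progression to more than 3 organ failures" (Section 5.3.3) simply by being connected. That needs the literal reading, and respiratory failure is excluded at entry, so three of the four other non-renal organs would have to be failing. The documents do not show that this is intended; they leave two passages unreconciled.

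**Conclusion.** The point holds for values after the first session and until washout: Days 2 and 3, possibly Day 5, and any later treatment day if a cycle restarts. There, DIALIVE-arm creatinine, MELD, kidney sub-score, CLIF-C ACLF score and ACLF grade cannot be told apart from device clearance. The size is a fall in creatinine of about 23-33% per session from dialysis flow alone, and 51-66% at maximum flows. CLIF-C ACLF falls by 3.3 to 6.6 points where a threshold is crossed. These figures rest on the assumed volume of 37.5 to 45 L and full saturation of the effluent; the washout example also assumes 1 g/day generation and constant native clearance.

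It would go too far to call the changes artefacts, since true renal improvement may occur at the same time. Days 14 and 28 are largely clean, as is Day 10 when no session was recent. The primary safety endpoint is not directly affected. Under the literal reading of Appendix 1b the score bias reverses sign, which is why the scoring rule has to be written down.

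**What to change.** 1. **Scoring rule.** State in Appendix 1b that, for endpoint scoring, a DIALIVE session is not scored as renal replacement, while CRRT given for renal failure is, in both arms.
2. **Visits that carry the comparison.** Rest between-arm conclusions on creatinine, MELD, CLIF-C ACLF score and ACLF grade on off-device visits: Day 10 if there was no recent session (interval fixed in advance), Day 14 and Day 28. Flag Days 2 to 5 and any treatment-day value as on-device, and do not present them as evidence of organ improvement. Session dates are already recorded (Section 7.1.1), so the flag can be derived.
3. **Context.** Report CRRT use by arm beside these endpoints, because SOC patients on CRRT score 3 while DIALIVE patients spared it do not.
4. **Reconciliation.** The sponsor must reconcile the renal-replacement wording in Appendix 1b with the rule on more than three organ failures in Section 5.3.3.

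The cost is one sentence, one derived flag and one extra table; no new visit is needed. The downside is that early time points carry less weight, and later ones lose patients to death or discharge.

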Appendix 2: a) AKI criteria for decompensated cirrhosis b) Lille score.

a. AKI criteria

The definitions of Acute Kidney Injury (AKI) grading are:

- o AKI stage 1A: acute rise in serum creatinine (sCr) of \geq 0.3 g/dl (27 µmol/L) in \leq 48 hrs, or sCr \geq 1.5 − 2 times the baseline sCr in 7 days (but absolute sCr value \leq 1.5 mg/dL AKI stage 1B: sCr > 1.5 mg/dL (134 µmol/L)
- AKI stage 2: $sCr \ge 2.1 3$ times the baseline sCr in 7 days
- O AKI stage 3: 3.1-4 times baseline sCr in 7 days, or sCr \geq 4 mg/L (354 μmol/L) with evidence of acute rise of \geq 0.3 g/dl (27 μmol/L) in \leq 48 hs

AKI stage 1B denotes significant kidney injury in the context of decompensated cirrhosis and equates to single renal organ failure or ACLF 1. AKI stages 2 and 3 should be used as per CLIF-OF score.

From: Huelin P, Piano S, Sola E, Stanco M, Sole C, Moreira R, et al. Validation of a staging system for acute kidney injury in patients with cirrhosis and association with acute-on-chronic liver failure. Clin Gastroenterol Hepatol 2017;15:438–445

b. Lille score.

Day 0 29 / 10 / 2018 (dd/mm/yyyy)

Date of Birth / / (dd/mm/yyyy)

Bilirubin | | | | | | | (dd/mm/yyyy)

| | | | | | | (at Day 0)

| | | | | | | (at Day 0)

| | | | | | (at Day 0)

Albumin* | | | | | | (at Day 0)

Patient's prothrombin time | | | | | (at Day 0)

^{*} In patients who have been treated with albumin infusions, in order to avoid the use of an artificial value, it is recommended to use the available albumin value before infusion of albumin

Lille Model Score = $(\exp(-R))/(1 + \exp(-R))$

Where R = 3.19 - (0.101 X age) + (0.147 X baseline albumin) + (0.0165 X change in bilirubin level) - (0.206 X creatinine) - (0.0065 X baseline bilirubin) - (0.0096 X prothrombin time)

From: Louvet A., Naveau S., Abdelnour M., et al. The Lille Model: a new tool for Therapeutic Strategy in patients with severe alcoholic hepatitis treated with steroids. HEPATOLOGY, Vol. 45, No. 6, 2007: 1348-1354.

Clinical Investigation Plan CIP YAQ-002 Version: 7.0 10 Octobe	er 2019
--	---------

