1. OVERALL SYNOPSIS OF THE CLINICAL INVESTIGATION

Title	A multi-centre, randomised controlled study, to evaluate the safety and performance of The DIALIVE Liver Dialysis Device (LDD) in alcohol related cirrhosis patients with Acute on Chronic Liver Failure (ACLF) versus standard of care (SOC).
Study Design	The design is a multi-centre, randomised, controlled, study to generate data for the evaluation of safety (as measured by the percentage of subjects who experience at least one serious adverse event (SAE), and performance (as measured by the lowering of the plasma endotoxin concentrations, and improved albumin function) of the DIALIVE in 30 evaluable patients with Acute on Chronic Liver Failure (ACLF) on the background of alcoholic cirrhosis versus standard of care (SOC).
Hypothesis	The hypothesis is that DIALIVE will significantly improve the prognosis of ACLF patients by modulating systemic inflammation.
Target Population	Men and Women ≥18 years, ≤81yr. Patients with a background of alcoholic cirrhosis who have either: 1. ACLF grade 1, ACLF grade 2 or grade 3a¹ as per CLIF-OF scoring system; OR 2Serum bilirubin > 20 mg/dL (342 µmol/L) as single organ failure²; OR 3. Stage 1b Acute kidney injury³. Treatment will be undertaken in an intensive care (ICU) or renal dialysis unit setting if the patients are randomised to the DIALIVE treatment arm. For patients randomised to the 'Standard of care' arm, the location of treatment (ICU or general ward) will be determined by their clinical need and will be decided by the site Principal Investigator.

_

¹ ACLF grade 3a patients, i.e. with 3 organ failures only, are included based on a favorable safety report by the Data Safety Monitoring Board following review of safety data on 12 ACLF grade 1 and 2 patients studied so far. ACLF grade 1 patients who have poor prognosis (28 day mortality > 15%) according to the more recent evidence, but were not identified within the original CANONIC study.

 $^{^2}$ Rapidly progressive hyperbilirubinaemia with serum bilirubin rising to > 20 mg/dL (342 μ mol/L)in ACLF is associated with high mortality, equivalent to ACLF 1.

 $^{^3}$ Recent data on Acute Kidney Injury (AKI) in decompensated cirrhotics suggest that even milder degrees of renal dysfunction (AKI 1b defined as serum Cr > 1.5 mg/dL or 134 μ mol/L) are associated with high mortality. AKI 1b does not constitute 'kidney failure' in the CLIF-OF scoring system.

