- 2. If the clinical condition of a patient meets one or more study stopping criteria.

Patients considered to be a 'screen failure' or 'excluded' will remain in study for a minimum follow up period of 28 days.

Standard definitions: definitions for DIALIVE organ failure and ACLF grading per the CLIF-C OF scoring system, Lille score, and others, are given in Appendix 1-2.

Hepatic Encephalopathy (HE): determination of HE as part of ACLF grading will be based upon clinical assessment and graded as per the West Haven criteria. However, if there is ambiguity or observer variability, an EEG may be sought by the PI for supportive evidence. This is particularly relevant for grade 1 HE which may not be consistenly reproducible using the West Haven criteria, and as such is now included as part of the covert HE spectrum along with minimal HE often requiring psychometric tests or EEG for diagnosis

Specific therapy such as corticosteroids for alcoholic hepatitis can be used if a patient is already within the study and these have not been trialed previously and as long as clinical justification and rationale is clearly documented. This applies to patients in both SOC and the DIALIVE arm. For other indications of steroid use such as potential relative adrenal insufficiency, it should precede a short synacthen test, particularly in patients who are haemodynamically stable, to establish this diagnosis.

Standard of Care (SOC) is defined as the standard medical and nursing management of patients with ACLF Grades 1 and 2 as per local practices. Medical intervention is to be guided by the treating physician taking into account the overall clinical picture, precipitating event, and the nature and severity of organ dysfunction. The interventions may include (but not limited to) the supportive management with fluid therapy, including albumin therapy where indicated, antibiotics for suspected or confirmed infections, nutrition, bowel management, thromboprohylaxis, and organ system support including the use of terlipressin as splanchnic vasopressor and for cardiovascular support where indicated, oxygen and non-invasive respiratory support, laxatives and non-absorbable antibiotics for hepatic encephalopathy, and dialytic therapy for renal failure. SOC may also include urgent liver transplantation as per local practices.

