5.3. Subjects

5.3.1. Inclusion criteria

- Male or female subjects aged ≥18 years ≤81yr
- Subject is able to provide informed consent to participate in the study, otherwise written informed consent must be
 obtained on behalf of the subject by next of kin or a legal representative in accordance with local ethical and legal
 requirements.
- History indicative of alcohol-related cirrhosis based on clinical, radiological and/or histological evidence.
- History of an acute decompensation event (including but not limited to ascites, gastrointestinal bleeding, hepatic encephalopathy and/or acute bacterial infections), occurring within ≤6 weeks of screening.
- Subject with :
 - o ACLF Grade 1, 2 or 3a defined per the CLIF-C OF score system OR
 - o single hepatic organ failure for serum bilirubin > 20 mg/dL (342 µmol/L) at screening and randomization, OR
 - \circ AKI-stage 1b (sCr > 1.5 mg/dL or 134 μ mol/L)¹².
- Where a subject has received corticosteroids for alcohol hepatitis and is deemed unresponsive to steroids after 7 days of treatment (lack of response defined as Lille score¹³ of > 0.45 or steroids stopped before 7 days due to any complication such as infection). This refers to the first course of corticosteorid therapy. Further courses of corticosteroids during the course of illness must not be used to determine steroid responsiveness.

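### Patients entering by AKI 1b or by bilirubin > 20 mg/dL alone have two possible ACLF grades, and no passage says which one the grade-based endpoints use

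*Protocol*

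**What the plan says.** Section 2.2 of the protocol refers the reader to Appendices 1 and 2 for "definitions for DIALIVE organ failure and ACLF grading per the CLIF-C OF scoring system". The relevant places are these:

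- **Synopsis, footnote 3:** "AKI 1b does not constitute 'kidney failure' in the CLIF-OF scoring system".
- **Appendix 1b, kidney row:** the lowest score, 1, is given for "Creatinine <2" mg/dL.
- **Appendix 1a, CLIF-OF subgroups:** a patient with no organ failure is No ACLF, as is one with a single hepatic failure, creatinine below 1.5 mg/dL and no encephalopathy. Renal failure is Grade 1. So are "Patients with other single failure organ failure with serum creatinine ≥1.5 and <2 mg/dl and/or HE grade 1-2".
- **Appendix 1a, study-specific column:** AKI 1b and bilirubin above 20 mg/dL are each listed as equivalent to Grade 1.
- **Appendix 2:** AKI stage 1B (creatinine above 1.5 mg/dL) "equates to single renal organ failure or ACLF 1".
- **Section 5.3.1:** entry by grade reads "ACLF Grade 1, 2 or 3a defined per the CLIF-C OF score system OR", with bilirubin above 20 mg/dL and AKI 1b as separate alternatives.

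The grade is then used in Section 5.1.3. Change in ACLF grade is a secondary endpoint, and endotoxin and albumin function are compared between arms among patients with the same grade. The schedules in Section 5.4 list ACLF grade at screening, Day 1 and each later visit to Day 28, without naming a grading rule.

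**The concern.** A grade-based endpoint needs one grading rule. Here the two newer entry routes carry a study-specific grade that differs from the grade given by the scoring system to which the protocol otherwise refers, and the reach of the study-specific grade is not stated. Three things are at stake:

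- the baseline grade reported for these patients;
- whether they belong in the Grade 1 comparison of endotoxin and albumin function, or in no grade stratum at all;
- whether a given clinical course counts as improvement in ACLF grade.

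The trial is open label with 15 evaluable patients per arm (5 cohorts × 3), so a few patients moved between strata would visibly alter the descriptive tables. The grading choice should therefore not be left to whoever fills in the form.

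**Working it through.** The protocol states no figure to reproduce, so the check applies each rule to constructed patients. The shading that marks organ failure in Appendix 1b is not visible in the text. Renal failure is taken as creatinine ≥ 2 mg/dL, in line with the renal entry in Grade 1 of Appendix 1a. The other failures are bilirubin > 12 mg/dL, West Haven grade 3–4, INR ≥ 2.5, and the circulatory criterion.

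**Grade at a single visit**

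| Patient | CLIF-OF subgroups | Study equivalents | Appendix 2 read as adding one renal failure |
|---|---|---|---|
| Creatinine 1.7, no other failure, no HE | No ACLF | 1 | 1 |
| Bilirubin > 20, creatinine < 1.5, no HE | No ACLF | 1 | not affected |
| Bilirubin 14, creatinine 1.7 | 1 | 1 | 2 |
| Liver and coagulation failure, creatinine 1.7 | 2 | 2 | 3a |
| Liver, coagulation and brain failure, creatinine 1.7 | 3a | 3a | 3b |

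The first two rows show the established conflict: one patient, two grades, a difference of one. The third row shows why the Appendix 2 sentence fits badly. Appendix 1a keeps that patient at Grade 1 and treats creatinine of 1.5 to below 2 as a modifier of the other failure. Counting AKI 1b as a renal organ failure would give two failures and Grade 2.

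**Change in grade, with one scheme applied at both visits**

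| Course (no other failure, no HE) | CLIF-OF subgroups | Study equivalents |
|---|---|---|
| Creatinine 2.5 → 1.6 | 1 → No ACLF: improved | 1 → 1: no change |
| Creatinine 1.7 → 1.5 or below | No ACLF → No ACLF: no change | 1 → No ACLF: improved |
| Bilirubin above 20 → between 12 and 20, creatinine < 1.5 | No ACLF → No ACLF: no change | 1 → No ACLF: improved |
| Creatinine 1.7 → 1.7 | no change | no change |

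The choice of scheme can thus move the count of improved patients in either direction, even when the scheme is held fixed across visits.

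**How many patients.** The protocol gives no frequency for either route. Footnote 1 of the synopsis describes the first 12 patients as ACLF grade 1 and 2. Appendix 7 agrees on the number: 14 enrolled less 2 non-evaluable = 12. The amendment history dates the AKI 1b and sole-bilirubin routes to version 6.0, which also reports the review after cohort 2. The upper bound is 30 − 12 = 18 evaluable patients, or 3 cohorts × 6.

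**The case against.** The strongest reply is that the passages can be read together. Footnote 3 is limited to the CLIF-OF system, and Appendices 1a and 2 speak of an equivalence. AKI 1b would then be no CLIF-OF failure but be treated as ACLF 1 in this study. That is fair, and a reader who infers a flat contradiction between footnote 3 and Appendix 2 overlooks the qualifier. The reading settles entry, however. It does not say which grade enters the endpoint tables.

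A reader might also infer a spurious one-grade improvement with unchanged creatinine, from the equivalent at baseline and plain CLIF-OF later. No passage prescribes such a switch, and with either scheme used throughout, an unchanged creatinine gives no change.

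A reader might further infer that eligibility turns on the page used, because three failures plus AKI 1b becomes 3b. That needs the additive reading in the last column of the first table. Appendix 1a argues against it, and so does the inclusion wording: AKI 1b would hardly need its own entry criterion if it already counted as an organ failure.

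Finally, all analyses are descriptive, one convention would apply to both randomised arms, creatinine and bilirubin are also reported separately, and a statistical analysis plan not shown here may fix the derivation. These points limit the consequences. They do not remove two differing definitions from the appendices to which Section 2.2 sends the sites.

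**Conclusion.** The point holds as a conflict of definitions that reaches a secondary endpoint and the same-grade comparisons. Its size is one ACLF grade per affected patient, in either direction for change in grade. The number affected cannot be computed. The ceiling of 18 evaluable patients assumes that the first 12 entered before the new routes existed, and any fraction of those 18 would be a guess.

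An effect on 3a/3b eligibility, or on the discontinuation rule in Section 5.3.3 that turns on more than three organ failures, is a possible reading and not an established one. It still calls for reconciliation, because Appendix 2 uses the language of organ failure and Section 2.2 makes that appendix part of the definition. Which clinical definition is right is not judged here.

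**What to change.** 1. State which scheme defines ACLF grade for change in grade and for the same-grade comparisons. Score every visit, including baseline, by that one scheme from the collected laboratory and clinical data. If wanted, show the other scheme as a descriptive sensitivity summary.
2. State whether the study-specific equivalence serves eligibility only or also grading after entry.
3. Reconcile Appendix 2 with footnote 3 of the synopsis and with Appendix 1a on whether AKI 1b counts in the organ-failure total, including for 3a/3b and the rule on more than three organ failures. The clinical choice is the sponsor's.

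The cost is a few sentences of protocol wording and regrading from data already scheduled for collection. No new assessments or patients are needed.
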